10.2.5 Methods and Testing procedure

Testing conditions (i.e. exam room, chart distance, lighting conditions) should remain constant for each ocular testing visit. Patients who wear eye glasses or contact lenses should wear them for each of the visual acuity and color vision assessments.

Best Corrected Visual Acuity (BCVA)

BCVA will be determined using a Snellen chart at a 10 foot testing distance under standard lighting conditions.

Patients will be instructed to begin at the top of the Snellen chart and read down the chart until they reach a row where all letters on a line cannot be read correctly. The smallest line that a subject can read correctly at the 10 foot distance will be recorded.

BCVA will be determined and recorded at Visit 2 (pre-dose), 24 weeks and 52 weeks or EOT.

Farnsworth-Munsell 100 hue test (F-M 100)

Color vision testing using the Farnsworth-Munsell 100 hue test will be used to evaluate color vision or color vision deficiency. It consists of 93 colors mounted in plastic caps of incremental hue variations, housed in four separate cases. Two caps are fixed as pilot colors at either end of the panel in each case. Patients will be asked to place the color caps in order of hue between each of the fixed anchors. The final arrangement of the hue caps represents the aptitude of the visual system in discerning differences in color hue.

The standard software application included in the F-M 100 package will be used for scoring and analyzing the results. Total error score (TES) will be used as a measurement of color vision. Total error score and level of color vision deficiency classification (e.g. superior, average, low discrimination) will be recorded on the eCRF.

Examination of color vision will be performed at Visit 2 (pre-dose), 24 weeks and 52 weeks or EOT.

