4. TREATMENTS

4.1 INVESTIGATIONAL TREATMENTS

BI 409306, as a film-coated tablet, will be produced by Boehringer Ingelheim Pharma GmbH & Co. KG.

Each film-coated tablet contains 50 mg BI 409306.

Eligible patients are randomly assigned to double blind treatment at a ratio of 1:1 of placebo or 50 mg b.i.d. BI 409306 (c.f. [Section 4.1.4](#) and [Table 4.1.4:1](#)).

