7.3.4 Safety analyses

Adverse events will be coded using the Medical Dictionary for Drug Regulatory Activities (MedDRA) coding dictionary. Standard BI summary tables and listings will be produced. All adverse events with an onset between start of treatment and end of the residual effect period (REP), a period of 7 days after the last dose of trial medication, will be assigned to the treatment period for evaluation.

All treated patients will be included in the safety analysis. In general, safety analyses will be descriptive in nature and will be based on BI standards. No hypothesis testing is planned.

Statistical analysis and reporting of adverse events will concentrate on treatment-emergent adverse events (i.e., by 'treatment at onset'). To this end, all adverse events occurring between start of treatment and end of the residual effect period will be considered 'treatment-emergent'. Adverse events that start before first drug intake and deteriorate under treatment will also be considered as 'treatment-emergent'.

Frequency, severity, and causal relationship of adverse events will be tabulated by system organ class and preferred term after coding according to the current version of the Medical Dictionary for Drug Regulatory Activities (MedDRA).

Laboratory data will be analysed both quantitatively as well as qualitatively. The latter will be done via comparison of laboratory data to their reference ranges. Values outside the reference range as well as values defined as clinically relevant will be highlighted in the listings. Treatment groups will be compared descriptively with regard to distribution parameters as well as with regard to frequency and percentage of patients with abnormal values or clinically relevant abnormal values.

Vital signs, physical examinations, or other safety-relevant data observed at screening, baseline, during the course of the trial and at the end-of-trial evaluation will be assessed with regard to possible changes compared to findings before start of treatment.

Descriptive statistics are planned to quantify the frequency of patients with suicidal ideation and behaviour as recorded on the C-SSRS at any post-baseline visit.

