10.2.3 Selection of Study Population

This sub-study will enroll approximately 50 patients from a subset of sites in the United States participating in the main study. Patients enrolled at the participating ocular sub-study sites will be required to complete all of the ocular safety assessments.

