10.2.6 Endpoint

Ocular safety will be assessed in a descriptive way based on change from baseline for the following endpoints:

- Best Corrected Visual Acuity test (BCVA) determined using a Snellen Chart
- Total error score from the Farnsworth-Munsell 100 hue testing (F-M 100)

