10.2.8 Statistical Considerations

Descriptive statistics for change from baseline will be presented. The descriptive statistics will include paired t-tests and confidence intervals.

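### The ocular sub-study records each patient's colour-vision class and Snellen line, but the readable plan names no analysis of the class and no count of patients who worsened

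*Protocol*

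**What the plan says.** Protocol 10.2 describes an ocular safety sub-study with tests at Visit 2 before the first dose, at week 24, and at week 52 or end of treatment. On size, 10.2.3 states: "This sub-study will enroll approximately 50 patients from a subset of sites in the United States participating in the main study".

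Two patient-level items are captured for colour vision (10.2.5): "Total error score and level of color vision deficiency classification (e.g. superior, average, low discrimination) will be recorded on the eCRF". For acuity, the same section states: "The smallest line that a subject can read correctly at the 10 foot distance will be recorded".

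Section 10.2.6 sets the basis of assessment: "Ocular safety will be assessed in a descriptive way based on change from baseline for the following endpoints". It then lists two items, best corrected visual acuity and the F-M 100 total error score. The classification is not listed. Section 10.2.8 plans descriptive statistics for change and adds: "The descriptive statistics will include paired t-tests and confidence intervals". It names no comparison between arms.

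For laboratory data, Protocol 7.3.4 asks that the arms be compared on distribution parameters and also on "frequency and percentage of patients with abnormal values or clinically relevant abnormal values".

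**The concern.** A drug-related loss of colour discrimination or acuity may well affect a few patients rather than shift the whole group. The natural question is then how many patients worsened by a relevant amount, and whether there were more on active treatment than on placebo. The data for that answer are on the eCRF, but the readable endpoint and statistics sections do not ask for it.

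The named inferential tools, paired t-tests and their intervals, act on the average change. Loss in one to three patients moves that average little and also inflates the SD. A non-significant result could be read as reassurance that it does not provide. This matters because Protocol 10.2.2 reports eye disorders as the most frequent adverse events in earlier studies, and gives further characterisation of ocular safety as the purpose of the sub-study.

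**Working it through.** The plan gives no power, precision, SD or threshold for this sub-study, so there is no stated figure to reproduce.

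**Inputs**
- About 50 patients (10.2.3) and 1:1 allocation (4.1), so about n = 25 per arm. Randomisation is not stratified by sub-study, so the split is approximate. n = 20 is also tried, as an assumed 20% loss.
- SD of change in total error score: not in the documents. Assumed 30 points, with normal changes.
- Harm: k patients in the arm each worsen by D points. Both values are assumptions.

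**Step 1: what the paired t-test sees.** The mean shift is kD/n. The expected variance of change becomes 30² + D²·k(n−k)/[n(n−1)].
- k = 2, D = 60: shift 2×60/25 = 4.8. Variance 900 + 3600×46/600 = 1176, SD 34.3, SE 34.3/5 = 6.86. Ratio 4.8/6.86 = 0.70.
- k = 3, D = 100: shift 3×100/25 = 12. Variance 900 + 10000×66/600 = 2000, SD 44.7, SE 8.94. Ratio 12/8.94 = 1.34.

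The two-sided 5% critical value on 24 degrees of freedom is 2.06.

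**Step 2: simulated chance of p<0.05** (200,000 runs, SD 30)

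| n per arm | Patients affected | Loss (points) | Paired t-test | Two-sample t-test |
|---|---|---|---|---|
| 25 | 0 | – | 5% | 5% |
| 25 | 1 | 60 / 100 | 5% / 5% | 5% / 5% |
| 25 | 2 | 60 | 7% | 7% |
| 25 | 2 | 100 | 9% | 8% |
| 25 | 3 | 60 | 12% | 9% |
| 25 | 3 | 100 | 16% | 14% |
| 20 | 2 | 60 | 8% | 7% |
| 20 | 3 | 100 | 17% | 15% |

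**Step 3: dependence on the SD.** If k equal losses grow very large relative to the SD, the t statistic tends to √[k(n−1)/(n−k)]. For n = 25 this is √(24/24) = 1.00, √(48/23) = 1.44 and √(72/22) = 1.81 for k = 1, 2 and 3. All are below 2.06. The insensitivity to one to three patients therefore does not rest on the choice of 30 points.

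**Step 4: what the other SAP summaries would show.** SAP section 7 gives a default set that includes the minimum, median and maximum. With 2 of 25 losing 3 SD, the median value of the worst change is about 3.6 SD, against 1.9 SD with no loss, and the worst value belongs to an affected patient in 95% of runs. So the extreme value would usually flag one case. The same section prefers median, quartiles and percentiles to minimum and maximum where data are extreme. With 2 of 25 losing 60 points, the median moves by about 0.10 SD (3 points) and the upper quartile by about 0.18 SD (5 points).

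**Step 5: what a patient count would give.** With n = 25, the chance of seeing at least one worsened patient, 1−(1−p)^25, is 40%, 72% and 93% for true rates p of 2%, 5% and 10%. With 0 of 25, the one-sided 95% upper limit is 1−0.05^(1/25) = 11.3%. With n = 20 the figures are 33%, 64% and 88%, and 13.9%.

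**Step 6: noise on placebo.** Under the same model, an unaffected patient worsens by more than 60 points (2 SD) with probability 2.3%. The chance that none of 25 does so is 0.977^25, about 56%. At a 30-point margin the expected number is 25×0.159, about 4.

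**The case against.** A reader might infer that ocular safety is judged on mean change alone and that individual losses are averaged away. The text does not support this. Section 10.2.8 plans descriptive statistics, of which the t-tests are a part, and the SAP default set includes the minimum and maximum. Protocol 5.3.6.2 has every vision-related adverse event recorded in the patient's own words, with ophthalmology assessment if severe or at the investigator's discretion. A data-monitoring committee also reviews safety. These routes stand. However, an extreme value identifies one patient, not the number who worsened or whether a class boundary was crossed. The SAP's preference for quartiles may remove the maximum when data are extreme. Adverse events depend on symptoms being reported.

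The absence may also be an artefact of redaction. The readable protocol goes from 10.2.6 to 10.2.8, several SAP contents entries are blacked out (one after the ECG section), and the SAP abbreviation list includes BCVA although no ocular analysis is visible. An unseen ocular analysis cannot be excluded.

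The laboratory comparison is not exact either. Laboratory values have reference ranges, and the sentence in 7.3.4 on other safety-relevant data asks only for changes from the pre-treatment findings. It shows that the protocol values patient counts, not that it breaks a rule of its own.

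Finally, the sub-study is descriptive, and 7.3.4 says that no hypothesis testing is planned for safety, so t-test power is not a design criterion. That is fair. The power figures matter only because paired t-tests are the inferential tool that 10.2.8 names.

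**Conclusion.** The point holds in a limited form. In the readable text, the F-M 100 classification is collected with no stated analysis, no relevant loss is defined for acuity or colour vision, and no count of worsened patients by arm is planned. The named tests respond to loss in two or three of about 25 patients in roughly 7% to 16% of cases, and to loss in one patient no more often than the 5% error rate. The exact percentages rest on the assumed SD and normal changes. The low sensitivity itself does not (step 3).

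Two stronger conclusions do not follow. The plan would not hide every individual loss, because extremes and adverse events would show some. Nor would a count necessarily show two or three affected patients against none on placebo: step 6 puts zero among 25 placebo patients at only about 56% for a 60-point margin. The documents give no class cut-offs, so the noise in a class shift table is unknown.

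The SAP (section 4) reports a much smaller trial than intended. If the sub-study also fell short, both the tests and the counts are weaker than shown. Confidence is medium because of the blacked-out text.

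**What to change.** Add to Protocol 10.2.6 and 10.2.8, and carry into the SAP, two tables by treatment arm:

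1. A shift table of F-M 100 class from Visit 2 to the worst post-baseline test, with the number and percentage moving to a worse class.
2. The number and percentage with acuity loss beyond a stated number of chart lines at any post-baseline test. The sponsor should fix that number before unblinding.

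Show exact confidence limits, compare the arms, and read the counts alongside the change summaries. If blacked-out text already specifies such tables, a cross-reference from 10.2.8 is enough.

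The cost is two small tables from data already on the eCRF, with no new tests or patients. The downside is imprecision: 0 of 25 still allows a true rate of about 11% (one-sided 95%). Taking the worst post-baseline test also admits some worsening from test variability, so a count in the active arm means little without the placebo count beside it.

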10.2.6 Endpoint

Ocular safety will be assessed in a descriptive way based on change from baseline for the following endpoints:

- Best Corrected Visual Acuity test (BCVA) determined using a Snellen Chart
- Total error score from the Farnsworth-Munsell 100 hue testing (F-M 100)

10.2.8 Statistical Considerations

Descriptive statistics for change from baseline will be presented. The descriptive statistics will include paired t-tests and confidence intervals.

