3. DESCRIPTION OF DESIGN AND TRIAL POPULATION

3.1 OVERALL TRIAL DESIGN AND PLAN

This is a multicentre, multinational, randomised, double-blind, placebo-controlled parallel group trial. In total, 300 patients with Attenuated Psychosis Syndrome (APS) are planned for randomisation in this study.

Patients are included in the study once informed consent/assent has been signed. Patients suitable after screening will be randomised to the 52 week treatment period assigned at a ratio of 1:1 to one of two treatment groups as shown in Figure 3.1: 1. Randomisation will be stratified by baseline use of antipsychotics (see [Section 7.6](#) for details). After completion of the treatment period, or following early discontinuation, patients will complete the 4 week follow-up period.

[figure not shown]

Figure 3.1:1 Overview of trial design

Additionally, exploratory biomarkers will be assessed for structural and functional measures of brain plasticity. These objective markers of brain physiology may help interpretation of the data or may help identify subgroups of patients that are better responders. The Biomarker Plan is described in [Section 5.5](#).

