7.6 RANDOMISATION

Patients will be randomised in blocks to double-blind treatment. Approximately equal numbers of patients will be randomised to each treatment group. The randomisation will be stratified by baseline use of antipsychotic medication. BI will arrange for the randomisation and the packaging and labelling of trial medication. The randomisation list will be generated using a validated system, which involves a pseudo-random number generator so that the resulting treatment will be both reproducible and non-predictable. The block size will be documented in the CTR. Access to the codes will be controlled and documented.

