7.7 DETERMINATION OF SAMPLE SIZE

Remission rate of the population diagnosed with APS and without intervention was assumed to be 40% ([R16-0991](#)) by 52 weeks. The rate of remission for BI 409306 was assumed to be 57% by 52 weeks. This will lead to a hazard ratio of 1.652.

Other study considerations are:

- Two-sided alpha = 0.10
- Dropout = 20% after one year
- Interim analysis checking for early efficacy using user-defined alpha-spending boundary of 0.01 at the 67% information point

Table 7.7: 1 Power calculations for sample size (for both arms combined) of 300 for various remission rates for BI 409306 with fixed placebo group aggregate first remission rate prediction of 40% by 52 weeks

Remission Rate for Placebo	Remission Rate for BI 409306	Hazard Ratio	Risk Ratio	Power for N=300	# Events needed in total
40%	52%	1.437	1.300	64.9%	126
40%	55%	1.563	1.375	81.5%	130
40%	57%	1.652	1.425	89.3%	133
40%	59%	1.745	1.475	94.4%	136
40%	61%	1.843	1.525	97.4%	139

[Table 7.7: 1](#) displays the power achieved for 300 total randomized patients given a group aggregate first remission rate of 40% for placebo with two-sided $\alpha = 0.10$ and a user-defined

alpha spending boundary at interim analysis of $\alpha=0.01$ (two-sided). Group remission rates for BI 409306 treatment of 52%, 55%, 57%, 59% and 61% are considered. Total number of events needed to achieve the power reported is also shown.

Given remission rates of 40% for patients treated with placebo and 57% for patients treated with BI 409306, the risk ratio is 1.425 (implying that patients treated with BI 409306 will have 42.5% more chance of achieving remission of APS compared to placebo). A sample size of 300 (or 150 per group) was selected as the most logical for establishing proof of concept based on the risk / benefit considerations noted above. In addition this was the sample size used in the previous protocol and is kept the same. This translates to 89% power. The type I error was selected to be 10% since this is a phase II study meant to provide an understanding of the effectiveness of the drug without being too strict as in a confirmatory setting.

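### The ocular sub-study names only paired tests of change from baseline, so a time or practice shift could be mistaken for a drug effect or could hide one

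*Protocol*

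**What the plan says.** Protocol 10.2.6 sets the aim: "Ocular safety will be assessed in a descriptive way based on change from baseline for the following endpoints". The two endpoints are best corrected visual acuity (BCVA) on a Snellen chart and the total error score of the Farnsworth-Munsell 100 hue test (F-M 100). Section 10.2.8 is two sentences long. It plans descriptive statistics for change from baseline and adds: "The descriptive statistics will include paired t-tests and confidence intervals". It does not say whether the tests are run by arm or on both arms together, and it names no contrast with placebo.

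On size, 10.2.3 says: "This sub-study will enroll approximately 50 patients from a subset of sites in the United States participating in the main study". Every patient enrolled at those sites must complete the ocular tests. They belong to the main trial, in which patients are "assigned at a ratio of 1:1 to one of two treatment groups" under double-blind conditions. Section 10.2.5 gives the timing for the F-M 100, and BCVA follows the same schedule: "Examination of color vision will be performed at Visit 2 (pre-dose), 24 weeks and 52 weeks or EOT".

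Two other places bear on the point. Protocol 7.3.4 says of safety analyses in general: "No hypothesis testing is planned". Protocol 10.1.8.2, for the exploratory EEG sub-study, plans a two-sided 95% confidence interval for adjusted differences between treatments.

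In the visible SAP, BCVA appears only in the abbreviation list.

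**The concern.** A paired t-test asks whether mean change differs from zero. The sub-study's objective is to characterise the ocular safety of BI 409306, which asks whether change differs from what would have happened without the drug. The two questions agree only if scores would otherwise stay still.

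That cannot be taken for granted. The F-M 100 is a performance task, ordering colour caps by hue, and is given up to three times over a year. Any learning or time trend acts in both arms. Randomisation lets the placebo arm remove it, but only if the analysis makes the comparison. A practice gain could hide a real worsening or look like an improvement on drug. A downward drift could look like harm. The placebo data are collected in any case, so the information is available at no extra cost.

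**Working it through.** The plan states no power, significance level, SD or sample-size rationale for this sub-study, so there is no figure of its own to reproduce. The check is how the named test behaves next to a between-arm comparison.

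**Inputs**
- About 50 patients (10.2.3) at 1:1 (3.1) give n = 25 per arm. This is approximate, because sub-study membership is not a stratification factor: "The randomisation will be stratified by baseline use of antipsychotic medication" (7.6).
- For week 52, 7.7 assumes for the main trial "Dropout = 20% after one year". Applied here, 25 × 0.8 = 20 per arm.
- Assumptions not in the documents: two-sided 5%; normal change scores with equal SD in both arms; a non-drug shift s common to both arms of 0.2, 0.3 or 0.5 SD of the change score.

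**Formulas**
- Paired test in one arm: t = mean change ÷ (SD/√n), with n − 1 df and noncentrality s√n.
- Between-arm test: t = difference in mean change ÷ (SD√(2/n)), with 2n − 2 df. The shift s cancels, so noncentrality depends only on the drug effect d: d ÷ √(2/n).

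**No drug effect.** At n = 25 the critical value is 2.064, and the noncentralities are 0.2 × 5 = 1.0, 0.3 × 5 = 1.5 and 0.5 × 5 = 2.5.

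| Probability of rejection | s = 0.2 | s = 0.3 | s = 0.5 |
|---|---|---|---|
| Paired, active arm, n = 25 | 16% | 30% | 67% |
| Paired, active arm, n = 20 | 14% | 25% | 57% |
| Paired, both arms pooled, n = 50 | 28% | 55% | 93% |
| Between arms, n = 25 or 20 | 5% | 5% | 5% |

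Simulation (40,000 runs) at s = 0.3 and 0.5 agrees: 30.3% and 67.1% for the paired test at n = 25, and 5.0% between arms.

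**Direction.** Nearly all paired rejections follow the shift. At n = 25, if the shift is a gain, a significant worsening appears in about 0.2% of trials at s = 0.2, 0.03% at 0.3 and under 0.001% at 0.5.

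**Reading two paired tests side by side.** With no drug effect, the chance that the active arm is significant and placebo is not is p(1 − p), where p is the paired rejection probability. At n = 25 this is 0.161 × 0.839 = 13.5%, 0.302 × 0.698 = 21.1% and 0.670 × 0.330 = 22.1%.

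**Masking.** Let the drug worsen the score by 0.5 SD and practice improve it by 0.5 SD. Net change in the active arm is 0, so the paired test rejects in 5% of trials. The between-arm noncentrality at n = 25 is 0.5 ÷ √(2/25) = 1.77, giving 41% power (34% at n = 20). With a practice gain of only half that size, the paired test rejects in 22.5%, and the between-arm power is still 41%.

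**Precision of the between-arm estimate.** The 95% half-width for an unadjusted difference in change is t × √(2/n): 2.011 × 0.283 = 0.57 SD at 25 per arm, and 2.024 × 0.316 = 0.64 SD at 20. The within-arm half-width at 25 is 2.064 ÷ 5 = 0.41 SD.

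**The case against.** The strongest reply is that nothing is decided on these tests. The sub-study is labelled descriptive, no significance level or action threshold is set, and 7.3.4 disclaims hypothesis testing for safety. By-arm tables would put placebo alongside. Ocular safety also has another randomised comparison: visual adverse events are recorded verbatim and adverse events are tabulated by treatment. For the transient events described in 10.2.2, those tables are the more direct evidence.

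Much of this stands, and it limits the point to a minor one. It does not remove it. Section 10.2.8 still names a test and an interval, neither of which addresses the drug question, and the t-tests sit badly with 7.3.4. Comparing significance between two tables is not a substitute for a contrast, as the 13.5% to 22.1% figures show. The EEG sub-study shows that an interval for the treatment difference is compatible with an exploratory purpose.

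Three further limits stand:
- That the tests are run within arms is the natural reading, not a stated fact. Pooling would be worse.
- Section 10.2.5 keeps testing conditions constant, which reduces some sources of shift, though not learning or time.
- Some SAP sections are not visible, including an entry after 7.8.4 in its contents list. BCVA is in the abbreviation list but nowhere in the visible body, so ocular analyses may be described there. SAP silence is not counted as an error.

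A reader might infer from the 16% to 67% range that the plan is likely to raise false alarms of ocular harm. The documents do not support that. Under a practice gain, the false signals are of improvement, and false harm is almost absent (0.2% or less). False harm at those rates would need a shift towards worse scores, and the documents describe none.

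**Conclusion.** The point holds as a conditional one. The protocol's only named inference for BCVA and F-M 100 ignores the randomised placebo group, and the visible text plans no treatment difference. A common shift could therefore be taken for a drug effect or could conceal one.

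The sizes are 16%, 30% and 67% paired rejection with no drug effect at shifts of 0.2, 0.3 and 0.5 SD (25 per arm), and 5% against 41% when a practice gain cancels a 0.5 SD worsening. They rest on assumed shifts, a two-sided 5% level and about 25 per arm. At a two-sided 10% level the first set becomes 25.5%, 42.7% and 78.3%. It would go too far to say that such a shift will occur: the documents give no estimate of one for either test.

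This is a low-severity matter in a descriptive sub-study of about 50 patients. The primary analysis is untouched.

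**What to change.** In Protocol 10.2.8, replace the paired t-tests with the baseline-adjusted BI 409306 minus placebo difference in change at weeks 24 and 52, with a 95% confidence interval. Present it as an estimate and not as a test, so that it agrees with 7.3.4. Specifically:
- F-M 100 total error score: ANCOVA on change, with the baseline score as covariate.
- BCVA: 10.2.5 records the smallest Snellen line read, so either convert lines to a numeric scale such as logMAR before the same analysis, or use an ordinal comparison.
- Keep within-arm change as summary statistics only.

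If a SAP section that is not visible already does this, 10.2.8 only needs to be brought into line with it.

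The cost is a sentence or two of text, with no new visits, patients or data. The downside is a wide interval: about ±0.57 SD at 25 per arm before any gain from baseline adjustment, about ±0.64 SD at 20, and wider still if the reduced trial size reported in SAP section 4 also shrank the sub-study. The difference detectable with 80% power is about 0.81 SD at 25 per arm and 0.91 SD at 20. The report should therefore say that an interval including zero is not evidence of no ocular effect.
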